The safety and efficacy of sufentanil have been demonstrated in different types of surgeries. After hip or knee arthroplasty, patients who received sublingual sufentanil reported lesser postoperative pain compared to placebo.¹⁴ Similar results were reported by patients who had undergone open abdominal surgery.¹⁵ Additionally, in one of the recent publications, the use of sublingual sufentanil in the preoperative period resulted in reduced opioid usage in the post-operative period and shorter time in the postoperative anesthesia care unit.¹⁶

In this case, series, we are testing the hypothesis that sublingual sufentanil (Dsuvia) will improve postoperative pain management in the PACU in ambulatory surgery patients taking Suboxone.

Primary Endpoint – We will evaluate the total amount of morphine equivalence (MME) in the perioperative period (defined as combined total opioid used intra-op and in the PACU).

Secondary Endpoint(s) – We will evaluate the time to fit to discharge from the PACU, the need for additional opioids and time to take the first additional opioid within 24 hours after being discharged from the hospital, and finally, the adverse events in the intraoperative period , PACU and in the 24 hours after being discharged from the PACU (i.e., nausea, vomiting, itching, hypotension, dizziness.)

Methods

Study Design:

Prospective case series study.

Inclusion criteria

- Age range 18-100 years
- Currently taking Suboxone
- ASA physical score 1-3
- Able to provide a signed informed consent
- General anesthesia (either endotracheal intubation or laryngeal mask airway) or **MAC** (**monitored anesthesia care**) without the use of regional anesthesia

Exclusion criteria

- Known allergic reactions to Dsuvia and its excipients
- Severe respiratory illness including exacerbation of asthma attack
- Significant intraoperative hemodynamic instability
- Use of Regional anesthesia techniques

Informed Consent

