The sponsor of the study is responsible for providing the study medication. The patient or the insurance will not be billed for the study medication. Study medication will be stored in the research pharmacy at Hutch. All appropriate storage instructions will be followed, and the pharmacist will be responsible for the drug audit. On the day of surgery for an enrolled subject, research personnel will retrieve medication from the pharmacy and deliver it to the physician for administration to subjects.

Sublingual sufentanil (Dsuvia) Study Protocol Pain Medications:

Pre-op:

Acetaminophen 975mg PO

Intra-op for induction (doses as per standard):

IV Midazolam

IV Fentanyl

IV Lidocaine

IV Propofol

After induction and before incision

Ketamine .35-.5 mg/kg IV

Dsuvia 30mcg SL (1st dose)

Postop:

If pain < or = 4/10,

Give no additional medications

If pain > 4/10

give Dsuvia 30mcg SL (2nd dose)

if 30 minutes after Dsuvia 2nd dose & pain is >4/10

give Ibuprofen 800mg IV

if 60 minutes after Dsuvia 2nd dose & pain is >7/10

give hydromorphone 0.4 mg IV

Interim Analysis

We are planning to conduct an interim analysis to evaluate the use of a single dose of Dsuvia in the intraoperative period. For this purpose, if 8 of the first 15 patients require a second dose of Dsuvia in the PACU, then the protocol will be changed to give the 2nd dose of Dsuvia in the OR at 15 minutes (or more) before extubating (and more than 1 hour since the 1st dose). The rest of the protocol will stay the same.

Comparison group

The comparison group in this study will be randomly selected from a cohort of the patients satisfying inclusion and exclusion criteria. The time frame for the comparison group will be the first Dsuvia patient to the last Dsuvia patient. For the comparison group, all the data points will be collected retrospectively. For comparison, group data points after the discharge from the hospital will not be collected. We are requesting a waiver of consent and HIPAA authorization for the comparison group as this will be

conducted retrospectively. A waiver will be needed because subjects may not be possible due to reasons such as relocation, wrong contract information given, or are no longer being seen at our institution.

Statistical analysis

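### The hypothesis is better PACU pain management, but no pain score is compared between groups and opioid is not given under a shared stated rule, so lower opioid use alone cannot show better analgesia

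*Combined protocol and SAP*

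**What the plan says.** All references are to the combined protocol and SAP.

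- **Hypothesis (end of the Introduction).** "sublingual sufentanil (Dsuvia) will improve postoperative pain management in the PACU in ambulatory surgery patients taking Suboxone".
- **Endpoints (same place).** The primary is MME, "defined as combined total opioid used intra-op and in the PACU". The secondaries begin "We will evaluate the time to fit to discharge from the PACU", then "the need for additional opioids and time to take the first additional opioid within 24 hours after being discharged from the hospital", and then adverse events. None is a pain score.
- **Tests (Statistical analysis).** A rank-sum test for opioid amount, and chi-square or Fisher for adverse events and for the number needing additional opioids. No test of pain is listed.
- **Pain data.** The follow-up described under Informed Consent includes a pain score at the 24-hour call. Under Comparison group: "For comparison, group data points after the discharge from the hospital will not be collected".
- **Dsuvia ladder (Study Protocol Pain Medications, Postop).** Pain above 4 brings Dsuvia dose 2. Thirty minutes later, pain still above 4 brings IV ibuprofen. Hydromorphone is given "if 60 minutes after Dsuvia 2nd dose & pain is >7/10".
- **Care replaced (Informed Consent).** Fentanyl 50 mcg as needed, during and after surgery, with no pain threshold. The section says pain guidelines will be standardized, but no rescue rule is written for the comparison group.
- **Interim Analysis.** If dose 2 is needed in the PACU by 8 of the first 15 patients, "then the protocol will be changed to give the 2nd dose of Dsuvia in the OR at 15 minutes (or more) before extubating". The sentence goes on to require that more than an hour has passed since dose 1. Then: "The rest of the protocol will stay the same".

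**The concern.** Opioid consumption can stand in for pain control when both groups receive opioid under a similar rule, or when pain is reported beside it. Neither condition is met here. After dose 2, a Dsuvia patient with pain of 5 to 7 gets ibuprofen and no further ladder opioid. A comparison patient with the same pain may get fentanyl. The first patient uses less opioid and may be in no less pain, and the planned outcomes could count that as a success.

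The Introduction itself names uncontrolled postoperative pain as a risk in patients on buprenorphine, so under-treatment is the failure this study most needs to be able to see. Time to fitness for discharge is at most a partial check, because the discharge criteria are not given.

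**Working it through.** **The plan's own figure.** Statistical analysis assumes 70% PACU rescue, a 50% reduction (to 35%), two-tailed alpha 0.05, power 0.85 and 30 per group. The two-sided pooled formula gives 35 per group, and power at 30 is about 79%. That mismatch is a separate matter, and nothing below depends on it.

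**Step 1. Is any pain score available in both groups?** The 24-hour score exists for Dsuvia patients only. PACU scores must be taken in Dsuvia patients to run the ladder, but they are not named as data or as an endpoint, and nothing is said about PACU scores in the comparison group. So no pain comparison is planned.

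**Step 2. When does the above-7 rule limit opioid?**

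| Situation | First PACU response to pain above 4 | Further ladder opioid |
|---|---|---|
| Dsuvia, dose 2 not yet given | Dsuvia dose 2 (an opioid) | Hydromorphone if above 7 |
| Dsuvia, dose 2 given in OR after the switch | Ibuprofen, read literally | Hydromorphone if above 7 |
| Comparison | Fentanyl as needed | No threshold stated |

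Only the second row removes opioid from patients at 5 to 7 on first PACU treatment. It applies only if the switch occurs, and only to patients for whom an hour has passed since dose 1 with at least 15 minutes left before extubation.

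**Step 3. How likely is the switch?** P(at least 8 of 15), binomial: 0.11, 0.50 and 0.95 if the true need for dose 2 is 35%, 50% and 70%.

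**Step 4. Illustration for PACU rescue, with identical pain in both groups.** Assumptions, not from the documents: the 70% rescue rate is read as the share scoring above 4; scores are roughly normal with SD 1.5 to 3; cut points are 4.5 and 7.5; OR dose 2 and ibuprofen do not change pain.

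- Mean = 4.5 + 0.524 × SD, which is 5.29 at SD 1.5 and 6.07 at SD 3.
- Share above 7: r = 1 − Φ((7.5 − mean)/SD), which is 0.070 at SD 1.5 and 0.317 at SD 3.
- If q of the 15 later patients have dose 2 in the OR, the Dsuvia rescue rate is [(30 − q) × 0.70 + q × r]/30.
- At q = 15 and SD 1.5: (15 × 0.70 + 15 × 0.070)/30 = 0.385.
- At q = 8 and SD 1.5: (22 × 0.70 + 8 × 0.070)/30 = 0.532.

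Exact Fisher test, 30 v 30, comparison rate 0.70, probability of a significant result favouring Dsuvia:

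| q | Dsuvia rescue rate, SD 1.5 to 3 | Favours Dsuvia |
|---|---|---|
| 15 | 0.385 to 0.509 | 62% to 23% |
| 8 | 0.532 to 0.598 | 16% to 7% |
| 5 | 0.595 to 0.636 | 7% to 4% |
| 0 (equal rates) | 0.70 | 1.3% |

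At q = 15, if clinicians give off-ladder opioid to half of those at 5 to 7, the range falls to 7-16%.

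**Step 5. Primary MME.** The above-7 rule lowers PACU opioid, but MME also counts the protocol Dsuvia doses, including one moved to the OR. The documents give neither a conversion factor nor usual-care intraoperative use, so the sign of any net bias cannot be derived.

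**Step 6. Precision of a pain comparison.** Half-width = t × SD × √(1/n₁ + 1/n₂). With 30 v 30: 2.002 × 1.5 × 0.258 = 0.78 and 2.002 × 3 × 0.258 = 1.55 points. If only 20 comparison patients have scores: 0.87 to 1.74.

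**The case against.** The best defence is that this is a declared pilot, the above-7 threshold may be a deliberate opioid-sparing choice, and the first PACU response to pain above 4 is an opioid until the switch. All of that stands, and the ladder need not change. The pilot label does not remove the problem, because the plan still states a hypothesis about pain management and tests it between groups at p < 0.05.

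Four stronger readings are tempting, and the documents do not support them.

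- *After the switch, every later patient has two OR doses and only hydromorphone in the PACU.* The one-hour condition excludes shorter cases, and for patients under monitored anesthesia care the timing relative to extubation is undefined. Those patients may still get dose 2 in the PACU. Case duration is not given.
- *The primary MME is biased towards Dsuvia.* No direction can be shown (Step 5).
- *The ladder forbids further analgesia.* Nothing says so, and routine care is kept for enrolled subjects. Any extra opioid already falls within the MME definition.
- *Comparing pain would show that Dsuvia caused any opioid saving.* It would not. The Dsuvia regimen also lists acetaminophen, ketamine and ibuprofen, so equal pain with less opioid could come from any of them.

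The rescue illustration has limits too. It reads the 70% as a pain share, although the plan states it as a treatment rate. It also matters only if additional opioids includes PACU rescue, whereas the endpoint wording can be read as post-discharge only.

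**Conclusion.** The concern holds in this form: the plan cannot support a conclusion of better PACU pain management from lower opioid use alone, because no pain score is compared and the two groups do not receive opioid under a shared stated rule. That much rests on the text and needs no assumption.

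The size is not determined. The effect on PACU rescue ranges from none, if there is no switch, to the 23-62% in Step 4 if all later patients qualify under the assumptions there; the lower rows are as consistent with the documents. This is something the sponsor should correct, with medium confidence. It is a gap in what the results can mean, not a demonstrated bias in the primary analysis.

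**What to change.** Keep the ladder and its thresholds.

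1. Name PACU pain as a secondary endpoint in both groups: worst score, and last score before PACU discharge. Take comparison scores from the PACU record. Report the between-group difference with a 95% CI.
2. State that lower MME or less rescue will be read as better pain management only alongside that comparison, and that it cannot separate Dsuvia from the ibuprofen, acetaminophen and ketamine in the same regimen. No fixed margin is needed in a pilot.
3. If the switch occurs, also describe Dsuvia patients by whether dose 2 was given in the OR or in the PACU. With so few patients in each part, this is descriptive only.

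**Cost.** No added patients. Some extra chart abstraction, with some comparison scores possibly missing. The scores would be unblinded and non-randomised. At about ±0.8 to 1.6 points (assumed SD 1.5 to 3), the interval could reveal a large worsening but could not settle a small difference.

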We are conducting this study as a pilot study. This pilot study's sample size is calculated based on the assumption that approximately 70% of the patients receive at least one dose of rescue opioid in the PACU. As this drug's efficacy in reducing the rescue opioids used in the PACU in this population is not studied previously, we plan to use a 50% rate reduction for calculating the sample size in this pilot study. According to our calculation estimate, we need to study 30 patients (alpha=0.05 and 1-Beta=0.85) in each group. The study will not be powered for secondary outcomes.

Descriptive statistics will be used to report all baseline demographic and clinical characteristics such as (age, gender, type of surgery, medications, ASA status, comorbidities). The primary endpoint amount of opioids used in the perioperative period will be compared using Wilcoxon rank-sum tests, and categorical variables such as adverse events and the number of patients requiring additional opioids will be analyzed using chi-square analysis or Fisher's exact tests. All the analysis will be two-tailed, and a p-value of <0.05 is considered statistically significant.

Data Management

All study data will be collected and entered into the computer database. Each subject will be assigned to a random number code, and the key linking the code and the subject identifier will be stored in a locked cabinet. The computer database will be password protected and will be kept on the HIPAA compliant Montefiore drive. The research manager is responsible for auditing the consistency of the data transcribed from the paper CRF to the computer. A protocol violation log will be maintained, and all protocol violations will be reported to the IRB and DSMB. The planned interim analysis (halfway through the recruitment) will be mainly focused on the additional dose of opioids in the PACU rather than the efficacy of the NMB reversal.

DSMB

The data safety monitoring board will be comprised of an anesthesiologist and a surgeon. All unanticipated serious adverse events will be reported to the DSMB. In the event of unanticipated serious adverse events, the continuation of the study will be at the discretion of DSMB and IRB. Periodic DSMB meetings will evaluate the occurrence of any study-related adverse events.

Human Safety

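### If a PACU Dsuvia tablet counts as rescue, the interim switch changes what the PACU rescue count measures in the Dsuvia group only, and a pooled p<0.05 test can then favour Dsuvia because of the rule change

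*Combined protocol and SAP*

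**What the plan says.** All references are to the combined protocol and SAP.

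- **Pain medication schedule (Postop).** At pain >4/10 the patient receives the second Dsuvia tablet. If pain is still >4/10 thirty minutes later, ibuprofen follows. The last step, hydromorphone, applies "if 60 minutes after Dsuvia 2nd dose & pain is >7/10".
- **Interim Analysis.** "if 8 of the first 15 patients require a second dose of Dsuvia in the PACU, then the protocol will be changed". The second tablet is then given in the OR, at least 15 minutes before extubation and more than 1 hour after the first. Everything else is left as it was.
- **Statistical analysis.** The study is sized on the assumption that "approximately 70% of the patients receive at least one dose of rescue opioid in the PACU", and "we plan to use a 50% rate reduction for calculating the sample size in this pilot study". It concludes that "we need to study 30 patients (alpha=0.05 and 1-Beta=0.85) in each group". On testing, "the number of patients requiring additional opioids will be analyzed using chi-square analysis or Fisher's exact tests", and "All the analysis will be two-tailed, and a p-value of <0.05 is considered statistically significant".
- **Data Management.** The interim is described as looking mainly at the additional PACU opioid dose.
- **Comparison group.** Comparators are drawn retrospectively over the same calendar period. Their post-discharge data are not collected.

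The plan does not define rescue opioid. It does not say how Dsuvia patients treated before and after a switch are to be combined.

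**The concern.** Before the switch, a Dsuvia patient with PACU pain of 5 to 7 out of 10 receives a PACU opioid, the second tablet. After the switch, a patient with the same score who has had that tablet in the OR has only ibuprofen available below the >7/10 step. If the PACU tablet counts as rescue, the first patient is an event and the second is not. Nothing comparable changes for the comparators.

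The change is also not neutral in timing. It is made only when PACU opioid need in the Dsuvia group is high, so the count becomes harder to meet when Dsuvia is doing badly on it. A test that pools all 30 Dsuvia patients could report a reduction in PACU rescue that comes from the change of rule. At stake is the outcome on which the study was sized.

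**Working it through.** **1. The plan's own figure.** Inputs are 70% against 35% (the 50% reduction read as relative), two-sided alpha 0.05 and power 0.85. The pooled normal formula is

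n = [1.960·√(2·0.525·0.475) + 1.036·√(0.70·0.30 + 0.35·0.65)]² / 0.35² = 35 per group.

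The stated 30 is not reproduced; power at 30 is about 79%. This is a side matter. It does show that the sizing rests on a single-stage comparison of PACU rescue proportions.

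**2. Chance that the switch fires.** Read the trigger as 8 or more of 15, with X ~ Bin(15, p).

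| True PACU opioid rate p | P(X ≥ 8) |
|---|---|
| 0.35 | 0.113 |
| 0.50 | 0.500 |
| 0.60 | 0.787 |
| 0.70 | 0.950 |

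**3. Model for no true effect.** Comparators ~ Bin(30, 0.70). First 15 Dsuvia patients ~ Bin(15, 0.70). If X ≥ 8, the last 15 ~ Bin(15, 0.70·h); otherwise Bin(15, 0.70). Here h is the share of >4/10 patients who would still reach the >7/10 hydromorphone step. The documents give no value for h, so a range is shown. It cannot exceed 1 in this model, because a score >7/10 is also >4/10. Further assumptions are that PACU tablets count as rescue, that moving the tablet brings no analgesic gain, and that every later patient meets the OR timing condition.

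**4. Size of the shift at h = 0.5.** The expected Dsuvia count is 10.5 + 0.95·(15·0.35) + 0.05·(15·0.70) = 16.0, against 30·0.70 = 21 comparators, with no difference in pain. With 21 comparator events, uncorrected chi-square is significant at 13 Dsuvia events: 60·(13·9 − 21·17)²/(30·30·34·26) = 4.34, above 3.84. At 14 it is not: 60·(14·9 − 21·16)²/(30·30·35·25) = 3.36. The shift therefore brings the expected count close to the boundary.

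**5. Exact enumeration.** Sum the joint probability of all outcomes with two-sided p<0.05 and fewer Dsuvia than comparator events.

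| h | Chi-square | Fisher |
|---|---|---|
| 1 (count unchanged) | 2.4% | 1.3% |
| 0.75 | 8.8% | 5.3% |
| 0.5 | 24.5% | 16.7% |
| 0.25 | 51.0% | 39.5% |

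At h = 1 the rejection rate in both directions together is 4.9% (chi-square) or 2.6% (Fisher), so the test itself behaves as intended when the count keeps one meaning.

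**6. Sensitivity.**

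- *Timing condition.* If only half of later patients meet it and the rest stay on the old schedule, the later rate at h = 0.5 is 0.70·(0.5·1 + 0.5·0.5) = 0.70·0.75. The result is that of h = 0.75: 8.8% (Fisher 5.3%).
- *Base rate.* At h = 0.5, 60% in both groups gives 13.0% (7.7%) and 50% gives 5.2% (2.7%).
- *Definition.* If only hydromorphone counts as rescue, the threshold is >7/10 before and after, and the switch does not move it.

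**The case against.** **The test may not be planned.** PACU rescue is not a listed endpoint. The phrase on patients requiring additional opioids resembles the secondary endpoint about opioids in the 24 hours after discharge. That reading fails for a comparison between groups, because the Comparison group section collects no post-discharge data for comparators. Data Management also uses the same idea, an additional opioid dose, for the PACU event that drives the interim.

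**Rescue might exclude the tablet.** Dsuvia is the study drug, so reducing rescue opioids could mean reducing other opioids. If so, the mechanism disappears. The interim wording favours counting the tablet but does not settle it, and this stands as a condition on the whole point.

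**The size rests on assumptions.** This also stands. The value of h is unknown. Patients given the OR tablet have had more opioid on board before the PACU, so a lower later count would mix any drug effect with the higher threshold. MAC and short cases may not fit the timing rule.

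**Non-randomised pilot.** A 5% error rate was never assured with retrospective comparators. That is true, but the plan still declares significance at 0.05, and this source of bias is separate and avoidable.

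**Stronger readings a reader might infer.** One is that the interim look uses up alpha. It does not: no groups are compared at the interim, and at h = 1 the error rate is unchanged. Another is that the primary result is compromised in the same way. It is not: the primary endpoint adds intra-operative and PACU opioid, so a tablet moved to the OR stays in the total and, given to more patients, would tend to raise Dsuvia MME.

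**Conclusion.** The concern holds conditionally. If PACU tablets count as rescue, the switch gives the rescue count two meanings within the Dsuvia group and leaves the comparators' count alone. At the plan's own 70% rate with no true effect, the switch is almost certain (0.95). The chance of a significant result favouring Dsuvia then runs from 2.4% to 51.0% by chi-square (1.3% to 39.5% by Fisher) as h falls from 1 to 0.25.

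It would go too far to say that the rescue test never has a 5% error rate. The inflation needs a base rate near 70%, h well below 1, and most later patients meeting the timing condition. With 50% in both groups, h = 0.5 gives only 5.2% (2.7%). If Dsuvia achieves the planned 35%, the switch fires just 11% of the time. The finding is limited to the PACU rescue comparison.

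**What to change.** In the Statistical analysis section, before the interim is carried out:

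1. State whether a Dsuvia tablet given in the PACU counts as rescue.
2. If the switch fires, report PACU opioid use separately for the first 15 and the later Dsuvia patients, each against comparators, with no p-value pooled across the switch. Add a note that the two periods have different opioid steps, and that the first 15 will by construction show at least 8/15 (53%) needing the tablet.
3. If one pooled test is wanted, use a single outcome defined identically in both groups and both periods. An example is any PACU pain score above 4/10 or any PACU opioid given, provided that comparator PACU scores can be read from the records. Applying such a definition to Dsuvia patients alone would not do: it would count pain scores in one group and opioid given in the other, and so introduce a new bias against Dsuvia.

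Items 1 and 2 cost a few sentences. Item 3 also needs a check that comparator scores are available. The price is less precision for the rescue comparison and a possibly less favourable rescue result. No dosing step changes.

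### The interim switch to a scheduled second Dsuvia dose turns on a dose count alone; no adverse-event review of the first 15 patients is required before it takes effect

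*Combined protocol and SAP*

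**What the plan says.** All references are to the combined protocol and SAP.

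- **Dosing before the switch** (Study Protocol Pain Medications). Every patient receives one 30 mcg dose after induction and before incision. In the PACU, a patient with pain of 4/10 or less falls under "Give no additional medications". A patient above 4/10 receives a second 30 mcg dose. If pain is still above 4/10 at 30 minutes, IV ibuprofen follows; if it is above 7/10 at 60 minutes, the instruction is "give hydromorphone 0.4 mg IV".
- **The switch** (Interim Analysis). The only stated condition is "if 8 of the first 15 patients require a second dose of Dsuvia in the PACU, then the protocol will be changed". The second dose is then given in the OR at least 15 minutes before extubation, "and more than 1 hour since the 1st dose". Everything else is to remain as it was.
- **Focus of the interim** (Data Management). "The planned interim analysis (halfway through the recruitment) will be mainly focused on the additional dose of opioids in the PACU".
- **Safety oversight** (DSMB). "All unanticipated serious adverse events will be reported to the DSMB", and after such events the DSMB and IRB decide whether the study continues. In addition, "Periodic DSMB meetings will evaluate the occurrence of any study-related adverse events". No meeting interval is given, and no meeting is tied to patient 15 or to the switch.
- **Adverse events collected** (Secondary Endpoints). Events are collected intraoperatively, in the PACU and for 24 hours after discharge, with the list "i.e., nausea, vomiting, itching, hypotension, dizziness".

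**The concern.** The switch adds no new dose level, since two 30 mcg doses are already allowed. It changes who gets the second dose and in what state. Before it, the dose goes to an awake patient who reports pain above 4/10. After it, the dose goes to a patient under anesthesia who cannot report pain, including patients who would have reached the PACU with pain of 4/10 or less and received nothing more.

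Patients who have had two doses among the first 15 are the trial's only own evidence on two doses when the decision is made. The rule counts them but does not ask what happened to them. The DSMB's periodic meetings may or may not fall before the change. At stake is a modest number of opioid doses, in ambulatory patients on Suboxone, that the pain rule would have withheld, given without a required look at data already in hand.

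**Working it through.** The plan states no operating characteristics for the 8-of-15 rule, so there is no figure to reproduce.

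**Inputs.** Trigger: 8 of 15, read as 8 or more (Interim Analysis). Dsuvia group: 30 patients (Statistical analysis), which leaves 30 − 15 = 15 after the look. The true second-dose rate p is not given and is an assumption. The sample-size paragraph plans on 70% of patients needing rescue opioid in the PACU and a 50% reduction, that is 70% × 0.5 = 35%. These describe rescue opioid rather than a second Dsuvia dose, so 35% and 70% serve only as stand-ins for the ends of a range, with 50% and 60% between. The PACU second dose is taken to be moved to the OR, not repeated.

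**Formulas.** With X ~ Binomial(15, p):

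- chance of switching = P(X ≥ 8)
- expected extra doses if switched = 15 × (1 − p)
- expected extra doses overall = P(X ≥ 8) × 15 × (1 − p)
- expected number of two-dose patients at a triggered look = E[X | X ≥ 8]

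| p | P(X ≥ 8) | Extra doses if switched | Extra doses, weighted | Two-dose patients at a triggered look |
|---|---|---|---|---|
| 35% | 0.113 | 9.75 | 1.10 | 8.5 |
| 50% | 0.500 | 7.50 | 3.75 | 9.1 |
| 60% | 0.787 | 6.00 | 4.72 | 9.7 |
| 70% | 0.950 | 4.50 | 4.27 | 10.7 |

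The weighted figure peaks at 4.74, at p of about 62%. If the look gives exactly 8 of 15 and later patients behave alike, the extra doses are 15 × 7/15 = 7.

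**Why these are upper bounds.** They assume that all 15 later patients can be given the scheduled dose. The rule needs more than 60 minutes after the first dose and at least 15 minutes before extubation, so more than 60 + 15 = 75 minutes from first dose to extubation. Shorter cases cannot meet this, and MAC cases, which the inclusion criteria allow, have no extubation to time from. Case lengths and the MAC share are not given. If 25% to 75% of patients could be scheduled (an assumption), the weighted figure at p = 60% falls from 4.72 to between 0.25 × 4.72 = 1.2 and 0.75 × 4.72 = 3.5; at p = 35% it falls from 1.10 to between 0.3 and 0.8. Hydromorphone avoided by the earlier dose is not offset against these counts.

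**What a review could show.** With 8 two-dose patients and an assumed event rate r, the chance of at least one event is 1 − (1 − r)^8: 15% at r = 2%, 57% at 10%, 83% at 20% and 94% at 30%. With no events, the one-sided 95% upper bound is 1 − 0.05^(1/n): 31% for n = 8 and 24% for n = 11.

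**The case against.** The strongest case is that the safeguards already exist. The DSMB includes an anesthesiologist, its periodic meetings cover any study-related adverse event, anticipated or not, and it shares discretion over continuation with the IRB after unanticipated serious events. The description of the interim as mainly about PACU opioid doses does not shut out safety data. The spacing condition is itself a protection that the PACU rule does not state. All of this stands.

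A reader might therefore be tempted to go further than the text and conclude that safety monitoring is missing, or that a cluster of anticipated opioid harm could not hold the switch back. The documents support neither. A periodic meeting could catch such a cluster, and nothing prevents the DSMB from acting on it. What the text lacks is only a requirement that a review come first. With no meeting interval stated, its timing relative to patient 15 is unknown.

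It is also fair to say that the review would be weak evidence. The Human Safety section puts the common events below 2%; at 2%, 8 patients show an event only 15% of the time. The two-dose patients received the dose awake and in pain, and some may also have had hydromorphone, so they stand in only indirectly for patients dosed under anesthesia. This limits the gain to catching gross harm. It does not argue against looking, because the data will exist and the board is already appointed.

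**Conclusion.** The point holds in a limited form. The switch depends only on how often a second PACU dose was needed, and no adverse-event review has to precede it. Its expected effect is at most about 5 additional doses among the last 15 patients once weighted by the chance of switching. The largest conditional figure, 9.8, goes with the least likely switch (11%). All the counts rest on assumed second-dose rates and on every later patient being schedulable. This is a cheap improvement to the timing of an existing review, of low severity; it is not a missing safeguard.

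**What to change.** Replace the automatic change with wording such as:

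> If 8 or more of the first 15 patients need a second PACU dose, the change takes effect only after the DSMB has reviewed intraoperative and PACU adverse events in those 15 patients by number of Dsuvia doses, including hypotension, oversedation and respiratory depression taken from existing records, and has agreed; until then patients stay on the original rule.

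Oversedation and respiratory depression are not named in the Secondary Endpoints list, which may be only illustrative. They should be abstracted from the intraoperative and PACU records so that the board has them. The plan should also state that a clean review does not show that two doses are tolerated.

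**Cost.** One sentence, two items from records that the plan already uses as a data source, and one re-timed or extra DSMB review. Recruitment need not pause. There are two downsides: the switch may be delayed for a few of the remaining 15 patients, so it no longer falls at a fixed patient number; and a clean result in about 8 to 11 two-dose patients may be taken for more reassurance than it carries.
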